9.4 STATISTICAL ANALYSIS PLAN (SAP)

This study will be analysed using the principles of the International Conference on Harmonisation E9 guidelines and reported according to the CONSORT guidelines. A full and detailed statistical analysis plan will be developed prior to the final analysis of the study. The main features of which are described here.

All analyses will be conducted on a Per Protocol population. All individuals in the control arm will qualify for the Per Protocol population. Individuals in the intervention arm will qualify for the Per Protocol population if they have at least one analysable Avantect test result (i.e. either “Detected” or “Not detected”). Per Protocol population will be analysed according to the original randomisation

group even when other aspects of the protocol are not followed e.g.unplanned cross-over, study withdrawal. It is expected that 98.8% of the randomised population will qualify for the Per Protocol population.

The co-primary outcomes are Avantect sensitivity and specificity in detecting PC, and resectability rate. Sensitivity is defined as the proportion of participants in the intervention arm with one (or more) Avantect “detected” test results who have pancreatic cancer diagnosed via imaging in relation to all individuals in the intervention arm who had pancreatic cancer diagnosed. Specificity is defined as the proportion of participants in the intervention arm with one or more Avantect “not detected” test results, and no Avantect “detected” results, who did not have a pancreatic cancer diagnosis in relation to all individuals in the intervention arm who did not have a pancreatic cancer diagnosis. Resectability is defined as the proportion of PCs deemed resectable by the study MDT divided by the number of PCs and will be compared between arms. For all co-primary endpoints, a logistic model will be used to estimate uncertainty. At the stage 1 interim analysis, due to alpha spending to reach a cumulative total alpha of 0.025 for each co-primary endpoint, a one-sided 98.6% confidence interval will be calculated to estimate the lower-bound of the observed proportion. At the stage 2 final analysis, a one-sided 98.5 % one-sided interval will be calculated instead. Co-primary endpoints will also be assessed for regular oversight meetings, where a one-sided 95% confidence interval will be used.

At the stage 1 interim analysis, co-primaries will be considered ‘futile’, ‘promising’ or ‘efficacious’ according to the following table:

	Expected proportion	Futility threshold at stage 1	Promising result range at stage 1	Efficacy threshold at stage 1
Sensitivity	65%	<46.5%	46.5% to 63.1%	>63.1%
Specificity	95%	<92.0%	92.0% to 94.9%	>94.9%
Resectability	40%	<21.0%	21.0% to 38.1%	>38.1%

At the stage 2 final analysis, the sensitivity co-primary will be considered successful if a sensitivity of 49% can be ruled out with a one-sided p-value of 0.03 among participants in the intervention arm. Specificity will be considered successful if a specificity of 92% can be ruled out with a one-sided p-value of 0.03 among participants in the intervention arm. Resectability will be considered successful if the resectability rate in the intervention arm is higher than the rate in the control arm at a one-sided p-value of 0.03.

Secondary outcomes, in order of importance, are defined as follows, which all are calculated with a minimum of 90% power:

Stage shift - The analysis will be conducted by comparing the proportion of PC cases diagnosed at stage I/II vs III/IV between the intervention and control arms. A proportion of 60% (44/73 PCs) is expected in the intervention arm versus 35% (26/73 PCs) in the control arm, which provides 90% power at a one-sided alpha of 0.05. Stage shift will be considered successful if the proportion in the intervention arm is higher than the rate in the control arm at a one-sided p-value of 0.05.

PPV in detecting PC - The analysis will be conducted within the intervention arm. With a sample size of 7,500, PC prevalence of 1%, and 2.5% lost from the per protocol population, there will be an expected 410 individuals with an Avantect “detected - abnormal” result. 11.6% (48/410) are expected to have a PC. PPV will be considered successful if a null PPV of 5% can be ruled out at a one-sided p-value of 0.05.

NPV in ruling out PC - The analysis will be conducted within the intervention arm with a sample size of 7,500, PC prevalence of 1%, and 2.5% lost from the per protocol population, will be an expected 6,902 individuals without an Avantect “detected - abnormal” result. 99.6% (6,877/6,902) are expected to not have a diagnosis of PC. NPV will be considered successful if a null NPV of 99% can be ruled out at a one-sided p-value of 0.05.

Resection rate of PC. The analysis will be conducted by comparing resection between the intervention and control arms. With a sample size of 15,000, PC prevalence of 1%, and 2.5% lost to follow-up, there will be an expected 73 cases of PC in each arm. It is assumed that 5% of those deemed resectable will not undergo resection, for an expected rate of 38% (28/73) in the Intervention arm versus 13% (9/73) in the control arm. Resection rate will be considered successful if the proportion in the intervention arm is higher than the rate in the control arm at a one-sided p-value of 0.05.

For analyses of exploratory outcomes, the following applies:

Time-to-event outcomes (time to PC diagnosis and overall survival) will be analysed using a Cox regression model to determine the hazard ratio (and 95% confidence interval) between groups. This will be supported by a Kaplan-Meier plot for each group, median survival (and 95% confidence intervals), and estimates of 3-year survival (T0-T3) (alongside the difference in proportions and corresponding 95% confidence interval). The 6-item STAI will be analysed using a t-test or non-parametric suitable alternative if data are not normally distributed. Performance characteristics for high-grade neoplasia include sensitivity, specificity, PPV and NPV. They will be analysed as described

SAFE-D Clinical Performance Study Protocol Version 4, IRAS Ref: 326332 31-JUL-2025 Page 49 of 68

above, when high-grade neoplasia is also considered as Disease Positive, and when high-grade neoplasia alone (with the exclusion of pancreatic cancer) is considered as Disease Positive. Two-sided p-values will be presented for exploratory outcomes.

Unless otherwise stated, continuous data will be presented as means and standard deviations and analysed using a linear regression modelling framework. If data are skewed, medians and ranges will be presented. To analyse skewed data we will attempt to find a suitable transformation to allow a linear modelling approach. If this is not possible, we will explore whether another suitable parametric distribution fits the data. If not, a non-parametric approach, such as quantile regression, will be used. Binary data will be reported in terms of odds ratios and analysed using logistic regression modelling, unless otherwise stated.

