2.4 TABLE OF ENDPOINTS/OUTCOMES PILOT

	Objective	Outcome Measures	Summary method(s)
Primary	To determine the recruitment rate	Recruitment rate	
 Percentage recruited of all participants invited Number of individuals recruited per month

STUDY STAGE 1 and 2 (analysis inclusive of pilot):

	Objective	Outcome Measures	Summary method(s)
Primary	To estimate the proportion of PCs deemed resectable	Resectability rate	Percentage of PCs deemed resectable by the study MDT [compared between arms]
	To estimate the sensitivity of the Avantect test in detecting PC	Sensitivity	Percentage with PC diagnosed who have an Avantect “detected” result [within intervention arm]
	To estimate the specificity of the Avantect test in ruling out PC	Specificity	Percentage without PC diagnosed who have one or more Avantect “not detected” results and no Avantect “detected” results [within intervention arm]
Secondary	To determine the effect of the Avantect test on PC stage shift	Stage shift	Percentage of PCs diagnosed at stage I/II [compared between arms]
	To estimate the PPV of Avantect for detecting PC	PPV	Percentage with an Avantect “detected” result who have PC diagnosed [within intervention arm]

	To estimate the NPV of Avantect for ruling out PC	NPV	Percentage of individuals with no Avantect “detected” test results who have no diagnosis of PC [within intervention arm]
	To estimate the proportion of PCs that are resected	Resection	Percentage with PC who underwent resection [compared between arms]
Exploratory	To estimate the time from NOD diagnosis to PC diagnosis	Time to diagnosis	Kaplan-Meier curve Hazard ratio [within intervention arm]
	To estimate the overall survival of study participants	Overall Survival	Kaplan-Meier curve Hazard ratio [compared between arms]
	Assess the effect of the Avantect test on state anxiety over time	6-item STAI	T-test or non-parametric alternative if suitable [compared between arms]
	To investigate the performance characteristics for high-grade neoplasia	Sensitivity Specificity PPV NPV	As described above, but disease positive is defined as PC and/or high-grade mucinous cysts and non-cases defined as no pancreatic cancer or high-grade mucinous cysts. This will be repeated where high-grade mucinous cysts are considered as disease positive and PCs are excluded. [within intervention arm]

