Streck® tubes will be processed to plasma within 24 hours of receipt in the WISH laboratory by trained operators and shipped at agreed frequencies as per the Laboratory Manual to ClearNote Health centralised laboratory (San Diego, California, USA). Streck plasma samples collected from patients randomised to the intervention arm will be analysed and results will be generated within 14 business days of receipt of arriving at Clearnote Health and “detected” test results will be reported to SCTU team by providing Avantect test results via an excel file and individual patient reports via secure file sharing (Safesend.soton.ac.uk). In the event of a sample failing predefined Avantect metrics, (expected failure rate is ~4%), the participant will be asked to return for a repeated draw (if the participant is still within the 28 days time frame from the original blood draw). If the failure happens at T0 and no blood could be collected while the participant is still within 6 months of diabetes diagnosis timeframe the participant will be asked to come back at T1. If the failure happens at T1 or T2 and no re-draw was performed, the participant will remain in study. For participants assigned to the control arm, samples will be kept for future potential Avantect testing and/or future research.

Lithium heparin samples will be processed according to SAFE-D specific SOP at the WISH laboratory and stored for future research within the SAFE-D study (or future ethically approved research).

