7.4 REGISTRATION/RANDOMISATION PROCEDURES

Following informed consent, participants will be assigned a unique patient identification number via an independent, web-based system (www.imedidata.com) by a member of the clinical study team at the hub. This will be in the format of SFD-####-##### with the first four digits consisting of the site code, and the last five digits consisting of sequential numbering provided through imedidata.com. The patient identification number will be added to the signed consent form.

Following their T0 visit, participants will be randomised to the control or intervention arm (1:1 ratio) via www.imedidata.com by a member of the WISH Laboratory team as specified on the delegation log. Participants will not be informed which arm they have been randomised to. The randomisation list will be pre-generated with permuted blocks of differing lengths.

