Two of the three co-primaries are metrics of test accuracy. In practice test results will not be available for all participants due to machine failure, insufficient blood sample quality, shipping or processing, or participants being unable to provide a blood sample. To reduce the number of participants where no test results are available, three collection time points are included. In the case where a blood draw did not occur or the sample was not analysable following a scheduled visit, a repeat blood draw will be arranged. The expected proportion of participants who are expected to not have a single Avantect result is 2.5%.

Using the PropTestPower function in the R package EnvStats, it was determined that 73 individuals with pancreatic cancer are required in each arm to detect a change of resectability from 14% in usual care to 40% in the intervention arm. At the stage 2 final analysis, allowing for interim analysis, the overall power would be 96.5%. Allowing for 2.5% loss to arrive at the Per Protocol population (see section 9.4), this increases to 75 cases per arm (150 total), which at an event rate of 1% leads to a recruitment target of 7,500 per arm (15,000 total). As only samples from the intervention arm are to

be tested for the purpose of the analysis, with an anticipated test sensitivity of 65% and specificity of 95%, this leads to the following confusion matrix in the intervention per protocol group (7,312):

		Diagnostic status	
		Has PC diagnosis	Does not have PC diagnosis
Avantect test result	Detected	48	362
	Not detected	25	6,877

With 73 cases of pancreatic cancer of which $48/73 = 65\%$ were detected by the Avantect test, this would be sufficient to rule out a sensitivity lower than 42 % in the stage 2 final analysis at 96.5% power. On discussion with the FDA, a specificity of 92% would be considered acceptable within this clinical context. With 6,877 individuals without a pancreatic cancer diagnosis of which $6,877/7,239 = 95\%$ are expected to be detected by the Avantect test, more than 99% power is achieved to rule out a specificity lower than 92%.

Definition of ‘promising result’ in study stage 1 to guide progression to study stage 2

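### Arm comparisons rest on a population that drops untested participants from the intervention arm only, an exclusion after randomisation that probably flatters the test slightly

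*Protocol*

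**What the plan says.** Protocol section 9.4 sets one population for everything: "All analyses will be conducted on a Per Protocol population". The qualifying rule then differs by arm. For controls, "All individuals in the control arm will qualify for the Per Protocol population". For the other arm, "Individuals in the intervention arm will qualify for the Per Protocol population if they have at least one analysable Avantect test result".

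Section 9.4 adds that members of this population are analysed in the group to which they were randomised, even after cross-over or withdrawal. That governs people already in the set and does not bring back those left out of it.

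Several endpoints are compared between arms on this population. Section 2.4 marks the co-primary resectability rate, stage shift, resection, overall survival and the 6-item STAI as between-arm comparisons, and section 9.4 gives success criteria for the first three. Sensitivity, specificity, PPV and NPV are within the intervention arm.

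On timing, section 7.4 states: "Following their T0 visit, participants will be randomised to the control or intervention arm (1:1 ratio"). The Avantect result comes later. If the T0 sample fails and cannot be redrawn in time, section 6.1 says that "the participant will be asked to come back at T1".

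**The concern.** Having an analysable result is known only after randomisation, and the condition is applied in one arm. Control participants who would have had no usable result stay in; their counterparts in the intervention arm are removed. The two groups compared are then no longer the two groups that were randomised.

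There are two reasons to expect this to favour the test. First, an untested participant cannot have a cancer found early by the test, so removing such people removes dilution of any effect. Second, once the T0 sample has failed without a redraw, a first result requires the participant to survive, stay well enough and attend months later. Those who do not are dropped from the intervention arm only.

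The rule also sits awkwardly with other parts of the protocol. Section 7.8.1 keeps participants with a detected result in the analysis even if they decline imaging, and section 11 keeps participants given alternative care in the analysis as allocated. At stake are one co-primary endpoint, two secondary endpoints and two exploratory ones.

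**Working it through.** **1. Reproduce the plan's own figure.** Section 9.2 gives the share without any result: "The expected proportion of participants who are expected to not have a single Avantect result is 2.5" per cent. Section 9.4 states: "It is expected that 98.8% of the randomised population will qualify for the Per Protocol population".

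- Loss in the intervention arm only: (7,500 + 0.975 × 7,500) / 15,000 = 98.75%, which rounds to 98.8%.
- Loss in both arms would give 97.5%.

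The stated figure is therefore built on a one-arm exclusion, so the rule is not a slip of wording.

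**2. Size of the exclusion.**

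- Participants: 0.025 × 7,500 ≈ 188.
- Expected cancers at the planned 1%: 75 per arm, of which 0.025 × 75 = 1.875 are untested and 73.125 tested.

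**3. Effect on the proportions among cancers.** The planned rates (sections 9.2 and 9.4) are taken as the rates in tested cancers. All-randomised rate = (73.125 × tested rate + 1.875 × untested rate) / 75. Two cases are shown: untested cancers do as in usual care, or none has the favourable outcome.

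| Endpoint | Planned, intervention v control | Untested as usual care | None favourable | Overstatement (points) |
|---|---|---|---|---|
| Resectability | 40% v 14% | (29.25 + 0.2625)/75 = 39.35% | 29.25/75 = 39.0% | 0.65 to 1.0 |
| Stage I/II | 60% v 35% | (43.875 + 0.656)/75 = 59.4% | 43.875/75 = 58.5% | 0.6 to 1.5 |
| Resection | 38% v 13% | (27.7875 + 0.244)/75 = 37.4% | 27.7875/75 = 37.05% | 0.6 to 1.0 |

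**4. Effect on false-positive risk.** Suppose the test has no effect and no untested cancer is favourable. The tested rate becomes the control rate divided by 0.975 (for resectability, 14% / 0.975 = 14.36%). With 73.125 v 75 cases and a one-sided normal approximation:

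- resectability: 0.03 becomes about 0.035;
- stage shift: 0.05 becomes about 0.063;
- resection: 0.05 becomes about 0.057.

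For resectability, the same calculation gives about 0.040 with 5% untested and 0.053 with 10%.

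**5. Overall survival.** The documents give no mortality figures. Assume 3-year mortality m of 6 to 8% overall and m_e of 20 to 30% among the excluded, with no true effect. The cumulative mortality ratio is (7,500m − 188m_e) / 7,312 / m:

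- m = 6%, m_e = 20%: (450 − 37.6)/7,312/0.06 = 0.94
- m = 6%, m_e = 30%: (450 − 56.4)/7,312/0.06 = 0.90
- m = 8%, m_e = 20%: (600 − 37.6)/7,312/0.08 = 0.96
- m = 8%, m_e = 30%: (600 − 56.4)/7,312/0.08 = 0.93

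The standard error of the log hazard ratio is about √(2/600) = 0.058 at 8% and √(2/450) = 0.067 at 6%. The spurious effect is therefore roughly 0.7 to 1.6 standard errors. If the excluded had average mortality, the ratio would be 1.

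**6. Power on all randomised participants.** This uses 75 v 75 cases, the all-randomised rates in step 3 and a one-sided normal approximation without continuity correction:

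- resectability at 0.03: 95.1 to 95.6% (73 v 73 at 40% v 14% gives 95.9% by the same formula; the plan states 96.5%);
- stage shift at 0.05: 89.9 to 91.7%;
- resection at 0.05: 96.6 to 96.9%.

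**The case against.** A reader might infer that the bias can only help the intervention arm. The documents do not support that. Section 9.2 attributes missing results largely to machine failure, sample quality, shipping and processing, and section 6.1 adds postal delay and failed assay metrics. None of these is linked to prognosis, although section 9.2 also lists participants who cannot give blood. If untested participants had the same outcomes as tested ones there would be no bias, and if all untested cancers were resectable the all-randomised rate would be (29.25 + 1.875)/75 = 41.5%, a bias against the test.

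Selection through illness, death or withdrawal is also narrow. T0 blood is drawn before randomisation, so someone who dies or stops later normally still has a result, and two of the three withdrawal options in section 7.12 keep samples already collected for analysis. Exclusion generally needs a failed T0 sample, no redraw and nothing usable at T1 or T2. This set is closer to a modified intention-to-treat set than to a usual per-protocol set.

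A reader might also infer that the registry supplies every outcome for the untested. It supplies stage, treatment and death (section 7.6.4), but resectability comes from study-team review of scans (section 7.9.4), and complete withdrawers contribute no further data.

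Finally, the detailed analysis plan is not shown, so the absence of an all-randomised sensitivity analysis is no fault. All of these points stand as limits. None removes the rule that section 9.4 states for all analyses, or justifies it for comparing arms.

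**Conclusion.** The one-arm exclusion after randomisation is stated outright and confirmed by the plan's 98.8%. It is reasonable for the accuracy measures and wrong for the arm comparisons. The direction is an inference: likely, not certain, to favour the intervention arm.

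At the planned 2.5% the overstatement is about 0.65 to 1.0 points for resectability, 0.6 to 1.5 for stage shift and 0.6 to 1.0 for resection, provided untested cancers do as in usual care or worse. Against a planned 26-point difference in resectability this would not change the conclusion. The 2.5% is an expectation and not a cap, so the effect grows if more participants go untested. Exploratory overall survival is the most exposed in relation to its precision, with a null cumulative mortality ratio of about 0.90 to 0.96, but only under mortality figures assumed here.

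This is a should-fix: small at the planned loss, but nearly free to remove, and more credible if removed before outcomes are seen.

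**What to change.** In section 9.4, analyse resectability, stage shift, resection, overall survival and STAI on all randomised participants by allocated arm, subject to withdrawal of consent for data collection. Limit the requirement for at least one analysable result to sensitivity, specificity, PPV and NPV, and keep that set as supportive for the arm comparisons.

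State that resectability of cancers in untested intervention participants is assessed by the same route as for control-arm cancers. Registry linkage already covers stage, treatment and death.

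When the wording is revised, reconcile the case numbers. Sections 9.2 and 9.4 plan 73 cancers in each arm after a 2.5% loss, whereas a rule that keeps all controls implies about 75 in that arm.

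The cost is a wording change, collection of scans for about two more expected cancers, and slightly less favourable expected intervention rates. Power stays at about 95 to 96% for resectability, 90 to 92% for stage shift and 97% for resection.

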 - Sensitivity of Avantect test for detecting PC – number of individuals in the intervention arm with one or more Avantect “detected” test results and PC divided by the number of individuals in the intervention arm with PC.
 - Specificity of Avantect test for ruling out PC – number of individuals in the intervention arm with no Avantect “detected” test results, at least one Avantect “not detected” test result and no diagnosis of PC divided by the number of individuals in the intervention arm with no diagnosis of PC.
 - Resectability rate – number of individuals with PC deemed resectable by the study multidisciplinary team (MDT) divided by the number of PCs.

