7.6.4 Timepoint T3 (2 years after T2)

T3 refers to the three years of follow-up (following recruitment at T0) which will be collected via linkage with the cancer and mortality registry. At the time of writing the cancer registry is managed by the National Cancer Registration and Analysis Service which sits within NHS England, and the mortality register is managed by the Office for National Statistics but can be accessed through NHS England. Cancer and mortality registry data will still be required and sought even if the owner of the dataset changes in the future. A cancer and mortality registry download will be obtained on three

occasions: once 6,400 participants have been recruited, once 15,000 participants have been recruited, and at 3 years post last participant recruited.

Data Collection from Cancer Registry:

- Any cancer diagnosis (ICD10 C00-D48)
- Date of cancer diagnosis
- Site of cancer diagnosis
- Stage of cancer at diagnosis
- Histology of cancer
- Survival status
- Cancer treatments

Data Collection from Mortality Registry:

[figure not shown]
- Date of death
- Causes of death

The local site study team will collect and keep NHS number, address and contact details (including 1 or 2 phone numbers and an email address) from all participants. NHS numbers and dates of birth for all participants will be shared securely by site to the SCTU. SCTU will then pass on the NHS numbers and dates of birth to the administrators at the registries to allow them to perform registry searches on three occasions during the study. The local site team will also share with the SCTU study team, via secure email, the contact details (name, postal and email address) for a select number of participants (numbers to be defined) who have consented to optional further research questionnaire.

Addresses will be used by sites to contact participants with any Avantect “Detected” results by post. Phone numbers will be used by sites to contact participants if required throughout the study, including contacting participants to inform them of a “Detected” Avantect test if deemed more appropriate than by post alone (at the discretion of the clinical team).

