7.8 AVANTECT OUTCOMES AND FOLLOW UP FOR PARTICIPANTS IN THE INTERVENTIONAL ARM

7.8.1. Detected

The CI will request the SAFE-D site team to notify participants in the intervention arm with Avantect “detected” test results and their GPs of the result via letter and an optional phone call (at the discretion of the clinical study team). The CI will also request the site team to arrange an urgent suspected cancer referral (tumour specific pathway referral) to local hepatobiliary (HPB) service Local Collaborator for a pancreas MRI (or CT if MRI is contraindicated) and imaging will be scheduled as per standard of care for suspected cancer pathway.

If participant with Avantect “detected” test result is unable or unwilling to undergo imaging of pancreas, participant will be removed from further Avantect testing, but will be included in the analysis and any cancer and mortality registry searches.

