7.9 IMAGING RESULTS

7.9.1 Normal imaging outcome

If imaging did not show signs of pancreatic cancer or pancreatic cystic lesion with high grade dysplasia and/or neoplasia then the participant will continue with the remaining study visits.

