7.9.3 Abnormal imaging outcome showing pancreatic cystic lesion

For abnormal imaging outcomes showing a pancreatic cystic lesion, European or local guidelines will be followed.

IPMN or Mucinous cystic neoplasms (MCN) that, after surgical and histopathological evaluation, show a high-grade dysplasia phenotype will be considered as pancreatic cancer¹². Otherwise, low grade dysplasia and other non-mucinous cystic lesions will not be considered as pancreatic cancer.

Participants in the intervention arm with Avantect “detected” test results and for whom pancreatic cysts have been found by MRI/CT, and surveillance has been recommended, will continue study visits as scheduled and will be considered as non pancreatic cancer outcome regardless of the size of the cyst until proven otherwise by pathological examination (Appendix III)

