7.10 DEFINITION OF BIOPSY OUTCOMES

The categories of clinical diagnostic follow-up findings are defined as follows:

- Histologic findings show pancreatic cancer, any stage (I-IV) based on American Joint Committee on Cancer (AJCC) v8.0.
- Histologic findings are indeterminate
- Histologic findings are consistent with pre-neoplastic lesions (IPMNs, mucinous cystadenoma or with pancreatic intraepithelial neoplasia (PanINs)).
- Histologic findings are consistent with an inflammatory process (benign disease)

Overall, the reference method will be histopathologic confirmation of PC, and/or definitive imaging diagnosis of PC.

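### Section 9.4 limits the sensitivity numerator to cancers diagnosed via imaging but not the denominator, contradicting the endpoint definition in 2.2; read literally, this can only lower a co-primary or leave it unchanged

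*Protocol*

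**What the plan says.** Section 9.4 gives the analysis definition of the sensitivity co-primary. The numerator is participants in the intervention arm with at least one detected result "who have pancreatic cancer diagnosed via imaging in relation to all individuals in the intervention arm who had pancreatic cancer diagnosed". The specificity definition that follows in the same paragraph has no imaging condition.

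The other places that bear on this endpoint are worded differently:

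- **Section 2.2 (primary endpoints):** the numerator is people with one or more detected "test results and PC divided by the number of individuals in the intervention arm with PC". The route of diagnosis is not mentioned.
- **Table 2.4:** the summary measure is "Percentage with PC diagnosed who have an Avantect" detected result, again without a route.
- **Section 9.3:** test performance is summarised against the pancreatic cancer diagnoses collected by the time of analysis.
- **Section 7.10:** "the reference method will be histopathologic confirmation of PC, and/or definitive imaging diagnosis of PC".
- **Section 7.9.3:** mucinous cysts that, after surgery and histopathology, "show a high-grade dysplasia phenotype will be considered as pancreatic cancer".
- **Section 7.8.1:** if someone with a detected result cannot or will not be imaged, the "participant will be removed from further Avantect testing, but will be included in the analysis and any cancer and mortality registry searches".
- **Section 7.9.1:** if imaging is normal, "then the participant will continue with the remaining study visits".
- **Section 7.6.4:** the three years of follow-up are data "which will be collected via linkage with the cancer and mortality registry".

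**The concern.** A sensitivity is the test-positive part of a fixed set of cases. In 9.4 the numerator and the denominator are drawn from different sets. A participant with a detected result whose cancer is established by a route other than imaging is in the denominator but not in the numerator, and so is scored as a false negative although the test was positive. Under 2.2 the same person is a true positive.

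Sensitivity is one of three co-primaries that must all succeed (9.2), and it has a pass/fail rule at the final analysis and thresholds at stage 1 (9.4). Two definitions of one co-primary in the same protocol leave the choice open. If it is made once results are known, it can be questioned as data-driven.

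**Working it through.** **1. Which definition do the planning figures follow?** Inputs from 9.2: 7,500 per arm, 2.5% without an analysable result, 1% prevalence, 65% sensitivity.

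- Cases: 7,500 × 0.975 × 0.01 = 73.1, so 73.
- Test-positive cases: 0.65 × 73 = 47.5, printed as 48.
- 48/73 = 65.8%, printed as 65%.
- Power against the 42% null in 9.2, exact binomial, n = 73, true sensitivity 65%: 97.3% at one-sided 0.03 and 95.4% at 0.015. These lie either side of the stated 96.5%.

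The figures reproduce. The confusion matrix in 9.2 counts every detected case with a diagnosis as a true positive, so it follows 2.2 and not the wording of 9.4.

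**2. Does the protocol allow test-positive cancers not diagnosed via imaging?** Three routes are possible:

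- Cysts become pancreatic cancer under 7.9.3 only after surgical histopathology. Until then they are non-cancer whatever their size, so under the protocol's own rule imaging alone cannot make this diagnosis. This is the clearest group.
- Detected participants who are not imaged stay in the analysis (7.8.1) and may later be diagnosed without imaging.
- Detected participants with normal imaging (7.9.1) or indeterminate imaging (7.9.5) continue and may be diagnosed later. Their later diagnosis may or may not rest on imaging.

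**3. Size per case.** Let k be the number of detected cancers not diagnosed via imaging. Literal sensitivity is (48 − k)/73, so each case costs 1/73 = 1.4 points. The documents do not give k; the range below is an assumption. P-values are one-sided. Exact p is the binomial probability of at least 48 − k successes in 73. Normal p uses z = (p̂ − p0)/√(p0(1 − p0)/73), for example at k = 5 against 49%: (0.589 − 0.49)/0.0585 = 1.69.

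| k | Observed | Sensitivity | Exact p vs 49% | Normal p vs 49% | Exact p vs 42% |
|---|---|---|---|---|---|
| 0 | 48/73 | 65.8% | 0.003 | 0.002 | <0.001 |
| 3 | 45/73 | 61.6% | 0.020 | 0.015 | 0.001 |
| 4 | 44/73 | 60.3% | 0.035 | 0.027 | 0.001 |
| 5 | 43/73 | 58.9% | 0.057 | 0.045 | 0.003 |
| 8 | 40/73 | 54.8% | 0.191 | 0.161 | 0.019 |
| 9 | 39/73 | 53.4% | 0.261 | 0.225 | 0.032 |

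At the 0.03 criterion in 9.4, the planned result first fails against 49% at k = 4 (exact) or k = 5 (normal approximation). Against 42% it first fails at k = 9 (exact).

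**4. Effect on power if a share of detected cancers is excluded** (assumed shares; exact binomial, one-sided 0.03, n = 73):

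| Share excluded | Expected sensitivity | Power vs 42% | Power vs 49% |
|---|---|---|---|
| 0% | 65.0% | 97% | 77% |
| 2% | 63.7% | 95% | 69% |
| 5% | 61.8% | 91% | 56% |
| 10% | 58.5% | 78% | 34% |

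The 77% in the first row does not come from the imaging wording. It reflects the difference between the two nulls.

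**5. Stage 1.** Assume 3,200 × 1% = 32 cases. This is an upper figure, because 1% is a three-year rate. Then 0.65 × 32 = 20.8, rounded to 21, and 21/32 = 65.6% lies above the 63.1% efficacy threshold. One excluded case gives 20/32 = 62.5%, which lies below it.

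**The case against.** The best defence is that the phrase is loose wording in one sentence. Everything else (2.2, 2.4, 9.3, the confusion matrix in 9.2) points to the 2.2 reading, and a full analysis plan is still to be written. The number affected may also be close to zero. Every detected participant is referred for MRI or CT, willingness and eligibility for imaging is an inclusion criterion (5.3), suspicion on MRI leads to a staging CT (7.9.4), and histology in this pathway normally follows imaging. Even the cysts in 7.9.3 are first seen on a scan.

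Much of this stands. It limits the size of the effect and shows which definition was probably meant. It does not remove the contradiction, because 9.4 is the section that states the analysis and its success rule, and its wording differs from the endpoint definition.

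A reader might go further and infer that every cancer found through the registry is excluded from the numerator. The documents do not support that. The registry is a source of data, not a method of diagnosis; a cancer recorded there may have been diagnosed by imaging, and 9.4 does not say that the imaging must be study imaging.

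A reader might also infer that about five such cases would fail the trial. That holds only against the 49% null. Against the 42% null used for the sample size, 43/73 passes comfortably (exact p = 0.003).

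**Conclusion.** The inconsistency is real and is in the current text: 9.4 defines a co-primary differently from 2.2, 2.4, 9.3 and the planned 48/73, and it does not fit the reference method in 7.10. Followed literally, it scores some test-positive cancers as misses.

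It would be too strong to say that the wording biases sensitivity downward as an established fact. The restriction removes cases from the numerator and none from the denominator, so the effect is downward or zero. Its size depends on a count that the documents do not give and that may be small.

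The change from pass to fail rests on three assumptions: the planned 48/73, the 0.03 criterion, and the null chosen. On the exact test it takes 4 excluded cases against 49% or 9 against 42%. Which null applies is a separate conflict between 9.2 and 9.4. The point merits correction because the repair is trivial and the endpoint has a pass/fail rule; the documents do not show that a large bias is likely.

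**What to change.** Delete the words *via imaging* from the sensitivity definition in 9.4, or replace the sentence with a cross-reference to 2.2. Numerator and denominator then both count pancreatic cancer under the 7.10 reference method, using the diagnoses collected by the point of analysis as in 9.3.

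Do not add a 36-month cut-off for registry diagnoses as part of this correction. Section 7.10 contains none, and the last registry download is three years after the last recruit (7.6.4), so earlier recruits may have longer follow-up. A cut-off would be a new rule that could remove cases.

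The cost is two words in the next amendment, made before any outcome data are examined. It needs no new data, leaves the sample size unchanged and does not alter patient management. The planned 48/73 then agrees with the written definition.
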